Study Description:	The goal of this project is to pilot test CHEC (Collaborative Healthcare Encounters with Caregivers) in primary care. CHEC is brief intervention with two components: 1) a checklist to identify the needs and concerns of unpaid/family caregivers who accompany older patients (aged 65+) to their primary care visits and 2) accompanying Tip Sheet for clinicians.
Sample Size:	
N = 60 caregivers*
 
N = 60 patients*
 
N = 10 primary care clinicians
 
*Participants will be a part of a patient-caregiver dyad and will be recruited together.

Enrollment:	This study will enroll 60 patient-caregiver dyads and 10 primary care clinicians. It will screen up to 200 patients, up to 200 caregivers, and up to 15 clinicians.
Study Population:	Patient participants will include individuals who have upcoming appointments at the Center on Aging (COA) and are identified by COA clinicians as typically attending appointments with a family caregiver. Patient participants will vary in age, gender, race/ethnicity, and health conditions. Family caregiver participants will include caregivers of patients receiving care at the COA. They will also vary in age, gender, and race/ethnicity. The clinician sample will include individuals who provide care at the COA. Clinicians will vary in age, be enrolled regardless of gender, and include those who have patient visits scheduled for June 2021 – August 2022.
Enrollment Period:	14 months
Study Design:	Two group single-blind randomized pilot RCT collecting: 1) survey data, 2) audio-recordings, and 3) electronic medical record data.
Description of Sites/ Facilities Enrolling Participants:	Participants will be recruited and enrolled at WCM/NYP offices, specifically the Center on Aging.
Study Duration:	August 31, 2024
Participant Duration:	Providers – 14 months Caregivers – 6 months Patients – 1 month
Primary Objective:	To examine the feasibility and acceptability of implementing CHEC in primary care practice.

Secondary Objectives:	To examine the preliminary impact of CHEC on primary care visit communication (discussion of family caregivers' needs).
Exploratory Objectives:	Not applicable
Primary Endpoints:	Feasibility will be assessed by accrual rates and rate of intervention completion. Acceptability will be assessed by surveys assessing perceived helpfulness, satisfaction, length, and impact on workflows. Effectiveness will be measured by the number of checklists that result in a conversation about caregivers' needs/concerns.
Secondary Endpoints:	Not applicable.

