1.1.2 Hypotheses / Research Questions

Hypothesis 1: Greater than 70% of caregivers will perceive the checklist to be an acceptable length and easy to use.

Hypothesis 2: Greater than 70% of caregivers will report that the checklist is helpful in identifying their unmet needs and starting a discussion with providers.

Hypothesis 3: Greater than 70% of caregivers and providers will report that they desire to continue using the checklist in the future.

Hypothesis 4: The checklist will not significantly impact primary care workflow or visit duration.

Hypothesis 5: Discussion of caregivers' needs and concerns will occur more often in the intervention group than in the usual care group.

Hypothesis 6: Caregiver perceptions of visit communication will be more positive in the intervention group than in the usual care group.

2. Background and Significance

In the United States, nearly 8 million older adults rely on family and other unpaid caregivers (neighbors; friends) for assistance with their health care. These caregivers collectively provide 75-80% of the total care hours to community-dwelling older adults and fill multiple roles in the health care system: attending doctor's visits, coordinating care, and assisting with treatment regimens. The availability and adequacy of assistance provided by family and unpaid caregivers have direct implications for health care costs and quality of care of older adults. Yet, caregivers are not systematically identified in care delivery systems, and their abilities and needs are not routinely assessed. Caregivers receive inadequate preparation for the tasks they must assume. They report high levels of stress and are at risk for physical illness, depression and anxiety, and sleep disturbance. If these impairments and unmet needs are not assessed and addressed, they can impede the caregiver's ability to provide effective assistance to the older adult, ultimately leading to costly hospitalizations and nursing home placements. These caregiver factors (health impairments; unmet needs) are particularly influential in the context of dementia where patients require substantial caregiving assistance.

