3.1 Overall Design

Clinicians who see patients at the Center on Aging (COA) will be made aware of the study via individual meetings with co-investigators. These meetings will be by phone, Zoom, or in-person if/when feasible. Patients and caregivers will be identified through referrals from physicians practicing at the Center on Aging. They will be sent a recruitment letter in the mail one month prior to a co-investigator calling them to go over the screening and consent forms. Any study data collected for potential participants that do not meet eligibility will be immediately deleted. Informed Consent and HIPAA authorization for caregivers and patients, and informed consent for clinicians will occur orally over the phone or in-person at the COA just prior to in-person health visits when feasible as outlined in the Informed Consent section.

Patient-caregiver dyads will be randomized into either the CHEC (n=60; 30 caregivers and 30 patients) or control (usual care) condition (n=60; 30 caregivers and 30 patients). Randomization will occur through block randomization with alternative block sizes of 4 and 6 for each participating clinician.

Intervention Condition. Participants in the intervention condition will complete the Caregiver Checklist portion of CHEC at the beginning of their health visit. The participating clinician will then respond to the checklist following the guidelines on the accompanying Tip Sheet.

Control Condition. Caregivers in the control condition will receive their usual care from the participating clinician during the health visit.

Baseline (pre-visit). Caregivers in both conditions will be asked to complete identical pre-visit surveys. The survey will be scheduled to be completed over the phone, digitally on REDCap, or in-person depending on the participant's preference and COVID-19-related guidelines. We will ask about the participant's background, caregiving role, communication with providers, and feelings of caregiver preparedness. It will take approximately 20 minutes to complete. Medical chart abstraction will be used to collect patient's background characteristics, medications, diseases, and health events (e.g., hospitalization). Clinicians will complete a pre-intervention survey over the phone or in-person depending on the participant's preference and COVID-19-related guidelines. We will ask for the clinicians' personal characteristics and preparedness to assess and address caregivers' needs and concerns.

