7.2.5 Record Retention

Essential documents are those documents that individually and collectively permit evaluation of the study and quality of the data produced. After completion of the study, all documents and data relating to the study will be kept in an orderly manner by the Investigator in a secure study file. Essential documents should be retained for 2 years after the final marketing approval in an ICH region or for at least 2 years since the discontinuation of clinical development of the IP. In addition, all subject medical records and other source documentation will be kept for the maximum time permitted by the hospital, institution, or medical practice.

8. Statistical Considerations

Feasibility and acceptability will be examined by conducting frequency and descriptive statistics (i.e. mean, median, standard deviation, range) for enrollment rates and Likert-scale items assessing satisfaction with CHEC and perceived helpfulness.

Effectiveness will be measured by the number of completed checklists that result in a conversation with providers about caregiver needs and the receipt of relevant support. The effect of CHEC on the primary outcome variable, discussion of caregivers' needs, will be examined in a general linear mixed model with intervention group and time (pre-posttest) as fixed classification

factors, and individuals as levels of a random classification factor. The model will account for pre-intervention measures and will include a group x time interaction. Additional covariates (e.g., caregiver and care recipient age) and fixed classification factors (e.g., caregiver gender, race) will also be examined. Prior to model fitting, the distribution of all study variables will be assessed.

9. Adverse Event Reporting Requirements

Adverse event (AE) monitoring and reporting is a routine part of clinical research. Safety is monitored by evaluation of adverse events reported by subjects or observed by investigators or research staff, as well as by other investigations such as clinical laboratory tests, x-rays, electrocardiographs, etc.

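### The only listed effectiveness endpoint is a count that exists in the CHEC arm alone, while the two-arm outcome in Section 8 is not listed as an endpoint and has no stated data source

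*Combined protocol and SAP*

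**What the plan says.** - **Synopsis, Primary Endpoints:** "Effectiveness will be measured by the number of checklists that result in a conversation about" caregivers' needs. No denominator or comparator is given, and Secondary Endpoints are marked as not applicable.
- **Synopsis, Secondary Objectives:** "To examine the preliminary impact of CHEC on primary care visit communication", meaning discussion of caregivers' needs.
- **Section 1.1.2, Hypothesis 5:** discussion of caregivers' "needs and concerns will occur more often in the intervention group than in the usual care group".
- **Section 3.1:** "Participants in the intervention condition will complete the Caregiver Checklist portion of CHEC at the beginning of their health visit". Controls receive usual care. The instrument list in Section 3.2 B gives the checklist to CHEC caregivers and to clinicians, but not to control caregivers.
- **Section 8:** effectiveness is the "number of completed checklists that result in a conversation with providers about caregiver needs and the receipt of relevant support". The text then turns to a different variable, discussion of caregivers' needs: "The effect of CHEC on the primary outcome variable" is to be examined in a "general linear mixed model with intervention group and time (pre-posttest) as fixed classification" factors, with pre-intervention measures and a group-by-time interaction.
- **Possible sources:** Section 3.1 has the visit recorded for all participants, and Section 3.2 A has the recordings transcribed. Section 6.1 schedules one recorded visit. On surveys, Section 3.1 says: "Caregivers in both conditions will be asked to complete identical pre-visit surveys". Section 3.2 B lists separate Intervention and Control forms for the 1-week survey.

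**The concern.** The synopsis and Section 8 both say that effectiveness is measured by a count that can arise only in the CHEC arm. Such a count cannot separate conversations prompted by CHEC from those that would have happened under usual care. The trial randomises dyads to supply exactly that comparison.

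Section 8 points to the right comparison but leaves three gaps. The two-arm outcome is absent from the endpoint list. It is labelled primary while the objective it serves is secondary. Nothing says whether it comes from the recordings, a survey item or the chart, or on what scale. The missing source matters because it decides whether the specified model can be fitted. Left open, the source and the coding rule could also be settled after results are seen.

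**Working it through.** **1. The plan's own figures.** The allocation is 30 + 30 = 60 dyads, which agrees with the synopsis. The documents give no alpha, power, effect size or usual-care discussion rate, so there is no design calculation to reproduce. All rates below are assumptions.

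**2. What the count says about Hypothesis 5.** Assume 18 of 30 CHEC dyads have a checklist followed by a conversation: 18/30 = 60%, exact (Clopper-Pearson) 95% CI 40.6% to 77.3%. The control rate is not given, so let it run over its full range. The difference is 18/30 - c/30, with a Newcombe 95% interval:

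| Control visits with discussion, c of 30 | Difference (points) | 95% CI |
|---|---|---|
| 0 | +60 | 39.0 to 75.4 |
| 6 | +40 | 15.3 to 58.6 |
| 12 | +20 | -5.0 to 41.8 |
| 18 | 0 | -23.5 to 23.5 |
| 24 | -20 | -40.6 to 3.2 |
| 30 | -40 | -57.7 to -20.9 |

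Worked row, c = 12. The Wilson limits are 0.423 to 0.754 for 18/30 and 0.246 to 0.577 for 12/30.
- Lower limit: 0.20 - √[(0.600 - 0.423)² + (0.577 - 0.400)²] = -0.050.
- Upper limit: 0.20 + √[(0.754 - 0.600)² + (0.400 - 0.246)²] = 0.418.

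The same one-arm count fits a large benefit, no effect or a deficit. This is not an estimate of bias. It shows that the count carries no information on the contrast.

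**3. Whether the Section 8 model can be fitted.** The fixed part has four columns: intercept, group, time and group × time.
- *Source is the recorded visit.* Every dyad has one value, at time = 1. The time column then equals the intercept column, and the group × time column equals the group column. The rank is 2 of 4. The sum of group and group × time, which is the arm difference at the visit, is estimable. Group alone, time alone and group × time alone are not.
- *Source is an item asked before and after the visit.* The rank is 4 of 4 and every term is estimable, provided both arms receive the same item. The pre-visit survey is identical in both arms. The 1-week forms differ by arm and their content is not in the document, so this cannot be confirmed.

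**4. Precision of a two-arm comparison.** Take control rates of 20%, 40% or 60% and a true difference of 0 or 20 points. As a crude check, the half-width is 1.96 × √[p₁(1 - p₁)/30 + p₀(1 - p₀)/30].
- 20% v 20%: 1.96 × √(0.32/30) = 20.2 points.
- 60% v 40%: 1.96 × √(0.48/30) = 24.8 points.

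A simulation of the Mantel-Haenszel risk difference (Sato variance) stratified by clinician used 60 dyads, 10 clinicians and alternating blocks of 4 and 6. It covered 3 control rates × 2 differences × 2 clinician SDs (0 or 1 on the logit scale) × 3 assumed volume patterns = 36 scenarios, with 50,000 runs each.
- Mean half-width was 18.5 to 25.0 points.
- Absolute bias was at most 0.13 points.
- Coverage was 92.7% to 94.1%.
- At least one clinician had dyads in only one arm in 0%, 28% or 81% of trials, depending on the volume pattern. The mean number of dyads dropped was 0, 0.5 or 1.9.

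**The case against.** The strongest reply is that Section 8 already plans the comparison. Straight after repeating the count, it models discussion of needs by intervention group, and that variable matches the secondary objective and Hypothesis 5. The count sits beside accrual and completion and can be read as a process measure. Recordings are a named data stream in both arms. The model problem arises only if recordings are the source, so replacing the model could discard a planned baseline adjustment. The trial is a pilot whose primary objective is feasibility and acceptability.

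Much of this is fair. A between-arm analysis is planned, and the model problem is conditional. The pilot setting limits the stakes.

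It does not remove the defect. Both places state in terms that effectiveness is measured by the checklist count. The two-arm outcome is still unlisted, inconsistently labelled and without a source. If recordings are the intended source, the specified interaction cannot be estimated; if they are not, the source is unknown. Either way the text has to change. Survey scales measured before and after the visit, including any used for caregiver perceptions under Hypothesis 6, can keep the mixed model.

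Three practical caveats also stand. The suggested interval covers slightly below 95%. The same clinicians, holding the Tip Sheet, see both arms, so spillover could dilute the difference. Recording is voluntary, so 60 coded visits is an upper figure.

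**Conclusion.** The concern holds. The only effectiveness endpoint in the synopsis has no control-arm value and cannot address Hypothesis 5. The two-arm outcome that could do so is outside the endpoint list, carries a label at odds with its objective, and has no stated source. These conclusions come from the text and need no assumption.

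The numerical illustration (+60 to -40 points) rests on an assumed 18 of 30 and an unrestricted control rate. The rank result applies only if the outcome is taken from the single recorded visit. No power, alpha or progression rule depends on the count, so this should be fixed but does not undermine the trial: it affects how preliminary impact is defined and reported.

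**What to change.** In the synopsis and Section 8:

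- **Define the preliminary-impact endpoint** as the proportion of index visits in each arm with any discussion of caregiver needs or concerns. Code it from the audio-recording in both arms by one written rule, under which naming the checklist alone does not count. Keep coders unaware of arm where possible.
- **Compare arms as randomised** by a risk difference with a 95% CI that accounts for clinician, the randomisation stratum. Mantel-Haenszel is one option. Clinicians with dyads in only one arm contribute nothing to it, so show crude counts by arm beside it.
- **Use this in place of the group-by-time model for this outcome**, and keep that model for survey scales measured before and after the visit.
- **Keep checklists followed by a conversation**, over all dyads randomised to CHEC, as a CHEC-arm process measure. Report receipt of relevant support separately.
- **Use one label**, primary or secondary, in the objectives, synopsis and Section 8.
- **Report missing recordings by arm.**

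The cost is wording in two places, a short coding rule, and coding of up to about 60 visits already due to be transcribed. Masking will be partial, because talk about the checklist can reveal the arm. A yes/no outcome ignores how much was discussed. The result may look less favourable than the one-arm count, with an interval of roughly ±19 to ±25 points under the assumed rates.

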1.1 Study Objectives

1.1.1 Objectives

Objective 1: To demonstrate the feasibility and acceptability of CHEC in primary care practice.

Objective 2: To test the preliminary impact of CHEC on primary care visit communication (discussion of family caregivers' needs).

1.1.2 Hypotheses / Research Questions

Hypothesis 1: Greater than 70% of caregivers will perceive the checklist to be an acceptable length and easy to use.

Hypothesis 2: Greater than 70% of caregivers will report that the checklist is helpful in identifying their unmet needs and starting a discussion with providers.

Hypothesis 3: Greater than 70% of caregivers and providers will report that they desire to continue using the checklist in the future.

Hypothesis 4: The checklist will not significantly impact primary care workflow or visit duration.

Hypothesis 5: Discussion of caregivers' needs and concerns will occur more often in the intervention group than in the usual care group.

Hypothesis 6: Caregiver perceptions of visit communication will be more positive in the intervention group than in the usual care group.

2. Background and Significance

In the United States, nearly 8 million older adults rely on family and other unpaid caregivers (neighbors; friends) for assistance with their health care. These caregivers collectively provide 75-80% of the total care hours to community-dwelling older adults and fill multiple roles in the health care system: attending doctor's visits, coordinating care, and assisting with treatment regimens. The availability and adequacy of assistance provided by family and unpaid caregivers have direct implications for health care costs and quality of care of older adults. Yet, caregivers are not systematically identified in care delivery systems, and their abilities and needs are not routinely assessed. Caregivers receive inadequate preparation for the tasks they must assume. They report high levels of stress and are at risk for physical illness, depression and anxiety, and sleep disturbance. If these impairments and unmet needs are not assessed and addressed, they can impede the caregiver's ability to provide effective assistance to the older adult, ultimately leading to costly hospitalizations and nursing home placements. These caregiver factors (health impairments; unmet needs) are particularly influential in the context of dementia where patients require substantial caregiving assistance.

Primary care practices are well positioned to aid in identifying and addressing the needs of at-risk family caregivers – in particular, persons who suffer from caregiving-related stress or have unmet needs for training or support – through systematic screening and referral. Nearly 40% of patients over the age of 65 are accompanied by a caregiver to routine medical visits. Primary care providers are often the first point of contact in the health care system for patients and caregivers, and thus have the opportunity to detect issues early in the caregiving trajectory. In addition, the long-term nature of the patient-caregiver relationship with a primary care provider affords the opportunity for periodic reassessment. This aspect is critical as the caregiver's needs change in response to the patient's physical health and cognitive function.

The objective of this project is to pilot test a novel screening-referral system for family caregivers who accompany older adults to their primary care visits. The long-term goal of this research is to develop a clinically feasible and scalable caregiver screening system that is acceptable to providers and caregivers. This system will set the stage for a sustained line of intervention work that connects at-risk caregivers with appropriate resources, services, and supports. From a clinical perspective, broad implementation of this system has the potential to reduce demands on primary care providers by directing caregivers to services designed to support their well-being and caregiving capacity.

3. Study Design and Methods

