- Patient data will be abstracted from the medical chart. Information obtained will include name, address, phone number, age, gender, race/ethnicity, provider, MRNs, electronic mail addresses and health diagnosis information including primary visit diagnosis code and clinic location (from defined time window), and health events (e.g. hospitalization, visit from home health aide). A partial HIPAA waiver will be requested for access to this information. All participants will be provided with a participant ID and their survey responses will be de-identified. Records will be maintained and kept in secure locations for a minimum of 3 years; the length of time specified according to WCM and HIPAA policies.

B. Study Instruments

The primary instruments for this study are validated, widely-used patient- and caregiver-reported outcomes (PCRO) assessments that are commonly used in health services research and clinical practice. These validated and reliable self-report measures include: Preparedness for Caregiving scale (Zwicker, 2010), CAPACITY measure (Van Houtven et al., 2019), Perceptions of Visit Communication (Talen et al., 2011), Caregiver Satisfaction with Primary Care Interactions (Clair et al., 2014; Haley et al., 1992), Perceived Self Efficacy in Primary Care Interactions (Maly et al., 1998), knowledge and use of resources (Thomas et al., 2017), caregiver anxiety and depressive symptoms (Mauer, 2012; Wild et al., 2014), and burden (Zarit, Reever & Bach-Peterson, 1980). We will use short forms when possible in order to reduce participant burden. We also developed several specific questions about caregivers' perception of the screening tool and knowledge of resources. All study instruments are attached to the IRB application in the WRG-HS system.

- Caregiver Subjects in CHEC (intervention group)

- CHEC Caregiver Screening Questions
- CHEC Caregiver Demographics
- CHEC Caregiver Pre-Test Questionnaire

- CHEC Visit Companion Checklist
- CHEC Caregiver 1-Week Post-Test Follow-Up Survey – Intervention
- CHEC Caregiver 2-Month Post-Test Follow-Up Survey – All Caregivers
- CHEC Caregiver 6-Month Post-Test Follow-Up Survey – All Caregivers
- Caregiver Subjects in control group
 - CHEC Caregiver Screening Questions
 - CHEC Caregiver Demographics
 - CHEC Caregiver Pre-Test Questionnaire
 - CHEC Caregiver 1-Week Post-Test Follow-Up Survey – Control
 - CHEC Caregiver 2-Month Post-Test Follow-Up Survey – All Caregivers

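### Can the 70% acceptability benchmarks in Hypotheses 1 to 3 be scored without a written scoring rule?

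*Combined protocol and SAP*

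**What the plan says.** Section 1.1.2 states three percentage benchmarks for acceptability:

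- The first concerns length and ease of use: "Hypothesis 1: Greater than 70% of caregivers will perceive the checklist to be an acceptable length and easy to use".
- The second concerns two kinds of helpfulness: "Greater than 70% of caregivers will report that the checklist is helpful in identifying their unmet needs and starting a discussion with providers".
- The third covers both groups of respondents: "Hypothesis 3: Greater than 70% of caregivers and providers will report that they desire to continue using the checklist in the future".

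The synopsis, under Primary Endpoints, lists the domains: "Acceptability will be assessed by surveys assessing perceived helpfulness, satisfaction, length, and impact on workflows". Section 8 (Statistical Considerations) plans frequencies and descriptive statistics for enrollment rates and for "Likert-scale items assessing satisfaction with CHEC and perceived helpfulness". It does not mention 70%.

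On the source of the data, Section 3.2 B says "We also developed several specific questions about caregivers" and their view of the tool, and adds that "All study instruments are attached to the IRB application in the WRG-HS system". The same section lists a separate intervention-arm version of the 1-week caregiver survey and a clinician post-test questionnaire. Section 3.1 gives the arm size as "CHEC (n=60; 30 caregivers and 30 patients") and has only the intervention condition complete the checklist.

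**The concern.** Acceptability is half of the primary objective, and these are its only percentage benchmarks. Three things appear to be missing.

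1. **The lists do not match.** The hypotheses cover five perceptions: length, ease of use, help in identifying needs, help in starting a discussion, and wish to continue. Section 8 names helpfulness, which covers two of them. The synopsis adds length. Ease of use and wish to continue appear only in the hypotheses, while satisfaction appears in both lists without a benchmark.
2. **The conjunctions are open.** Hypotheses 1 and 2 each join two perceptions. Read literally, the same caregiver must endorse both; item-by-item frequencies give each one alone. Hypothesis 3 joins two groups of respondents.
3. **No cut-off or denominator is stated.** The questions about the tool were written for this study, so no published threshold can be presumed.

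If these choices were made after the data were seen, the same answers could be reported as meeting or missing a benchmark.

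**Working it through.** The plan gives no sample size, power or precision calculation for these hypotheses, so there is no figure of its own to reproduce. The check asks how much the open choices can alter a result.

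**Inputs from the documents.** Benchmark above 70%; 30 CHEC-arm caregivers (Section 3.1); 10 clinicians (synopsis). Endorsement rates, correlations and the number of responders below are assumptions.

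**Smallest passing count.** 21/30 = 70.0% is not above 70%, so a pass needs 22/30 = 73.3%. For clinicians alone it is 8/10. The exact 95% intervals are 54% to 88% for 22/30 and 44% to 97% for 8/10, ignoring clustering by clinician.

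**Per item or jointly: bounds.** If each of two items is endorsed by m of 30, the number endorsing both lies between 2m − 30 and m.

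| m | both items, range | can the readings disagree? |
|---|---|---|
| 22 | 14 to 22 | yes |
| 23 | 16 to 23 | yes |
| 24 | 18 to 24 | yes |
| 25 | 20 to 25 | yes |
| 26 | 22 to 26 | no |

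So, with equal counts, disagreement is possible only at 22 to 25 of 30. The lower bound also needs an unusual pattern. At m = 24, a joint count of 18 means that no caregiver rejects both items, which is a correlation of (0.60 − 0.64)/0.16 = −0.25. Two views of one short checklist would more plausibly be positively related.

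**Per item or jointly: probabilities.** With true endorsement p on each item and correlation φ, P(both) = p² + φp(1 − p). The joint pass probability is binomial, and the per-item probability (both items at 22 or more) comes from the exact multinomial, n = 30.

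| p | φ | P(both) | joint reading passes | each item passes |
|---|---|---|---|---|
| 0.80 | 0 | 0.640 | 19% | 76% |
| 0.80 | 0.3 | 0.688 | 38% | 78% |
| 0.80 | 0.5 | 0.720 | 53% | 79% |
| 0.85 | 0.3 | 0.761 | 72% | 95% |
| 0.90 | 0.3 | 0.837 | 96% | over 99% |

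The readings diverge when endorsement is near the benchmark and converge as it rises.

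**Denominator.** With 26 responders (assumed), 19 to 21 agreeing is 73% to 81% of responders but 63% to 70% of 30. The documents narrow this choice. Only CHEC-arm caregivers complete the checklist, their 1-week survey has its own version, and Hypotheses 2 and 3 speak of what caregivers report. A percentage of responders is the ordinary reading.

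**Cut-off.** Section 8 describes Likert items only for satisfaction and helpfulness. Among the benchmarked perceptions that reaches Hypothesis 2. The documents do not say what response format length, ease of use or wish to continue have; a yes/no item would need no cut-off.

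**Hypothesis 3.** Pooling could pass with 25/30 caregivers and 4/10 clinicians: 29/40 = 72.5%. But the two groups answer separate instruments, and Section 2 aims for a system acceptable to both, so separate percentages are the natural reading.

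**The case for a change.** The strongest case for a change is that a benchmark stated in advance is worth little if its scoring is not also fixed in advance. The vulnerable range, 73% to 83% per item, is a plausible pilot result. At 80% endorsement and correlation 0.3, the choice of reading moves the chance of a pass from 78% to 38%. Even with the questionnaires in hand, Section 8 would not say which categories count, which denominator applies, or how the two parts of Hypotheses 1 and 2 combine. A remedy would cost one paragraph and no new data.

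The arithmetic stands, and so does the observation that no scoring rule is written down. Three things limit it. The unseen instruments may settle the items and response formats, and one question covering both halves of a hypothesis would remove the joint-or-separate issue for it. Imposing the both-items rule would be a substantive choice, stricter than the per-item rule (72% against 95% at 85% endorsement and correlation 0.3), and it belongs to the study team. And frequencies for each item, which Section 8 already plans for the items it names, would show readers most of what any cut-off concealed.

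**Conclusion.** No change to the plan follows. The missing scoring rule is a gap that analysts fill sensibly: tabulate each item among CHEC-arm responders, show counts and non-response, report caregivers and clinicians separately, and treat 70% as descriptive. Nothing in the plan directs a wrong calculation, and no test, power claim or go/no-go decision rests on the benchmark. Acceptability also draws on satisfaction, workflow impact and clinician interviews, so these percentages do not settle it alone.

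The effect is confined to results near 70%. For Hypotheses 1 and 2 with equal item counts, that means 22 to 25 of 30. Even there, an exact interval of 54% to 88% around 22/30 shows that a pass or a miss carries little information by itself. The mismatch between lists is a matter of brevity: length is in the endpoint list, and the absence of ease of use and wish to continue from a short analysis summary does not show that they go uncollected.

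This rests on full response from 30 caregivers where not stated otherwise, on the assumed endorsement rates and correlations, and on each item's counts being reported.
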